8.4 Analysis Populations

An Intention to Treat (ITT) population includes all patients who sign the consent and are assigned to a treatment regardless of the actual drug dose the patients receive. Safety analysis population includes all patients who receive at least one drug dose. Per Protocol

Population includes those who receive the prescribed dose of the drug per protocol and excludes patients who drop out of the study prematurely. Whenever possible, we will use the ITT population to analyze the primary and secondary endpoints provided that their primary and secondary endpoints are measured. As a secondary analysis, per protocol population will be used for the analysis of the primary and secondary endpoints. Safety analysis population will be used to analyze safety and toxicity data.

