3.5 End of Treatment Cycles

Patients who progress radiographically on ipilimumab after completion of the initial four doses will not receive more immunotherapy once progression has been documented. For soft-tissue lesions, the RECIST criteria for progression (see 6.4.2) will be used. For bone lesions, there should be ≥ 2 new lesions confirmed on a second scan at least 4 weeks later. Progression will not be assessed until completion of the initial 4 cycles of treatment in order to avoid premature discontinuation of therapy.

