5.1.4 Discontinuation of Study Therapy

Subjects MUST be discontinued from study therapy AND withdrawn from the study for the following reasons:

- Withdrawal of informed consent (subject's decision to withdraw for any reason)
- Any clinical adverse event, laboratory abnormality or intercurrent illness which, in the opinion of the investigator, indicates that continued treatment with study therapy is not in the best interest of the subject
- Termination of the study by Bristol-Myers Squibb (BMS).
- Imprisonment or the compulsory detention for treatment of either a psychiatric or physical (e.g., infectious disease) illness.
- Progression of disease, as defined by radiographic progression, **after 12 weeks of therapy**. Furthermore, all radiographic progression must be confirmed by a repeat scan done at least 4 weeks after the suspicious scan. Immune response is not a part of this algorithm.

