8.2 Primary and Secondary Endpoints

The primary endpoint is the achievement of an undetectable PSA defined as $PSA \le 0.2$ ng/mg after initiation of ipilimumab therapy. The secondary endpoints are: time to PSA progression, time to disease progression by any measure, time to death from any cause, number of patients with immune related Adverse Events (IRAEs), correlation between IRAEs and clinical outcomes, and the ratio of T regulatory cells to T effector cells, and additional measures of immune responses.

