8.3 Sample Size Justification

N=30 (for the final analysis, 10 for the intial analysis). Using the Simon two-stage design for Phase II trials, the initial accrual will be 10 patients. Assuming that 10% of patients receiving usual care will achieve an undetectable PSA (PSA \leq 0.2) without additional intervention, the trial has a 80% power to detect a rate of achieving an undetectable PSA of \geq 30% among patients treated with ipilimumab. At least two patients with an undetectable PSA will be required in the first 10 patients to continue to stage 2. As soon as two patients having achieved an undectable PSA are identified, stage 2 for of the study will begin. If 6 or more of 30 patients have achieved an undetectable PSA at 6 months, the study will be considered successful and the regimen worthy of further investigation. This design has a type I error rate of 0.05 and a type II error rate of 0.20.

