8.5 Statistical Analysis Plan

Demographic and clinical characteristics will be summarized using descriptive statistics (e.g. proportions, mean, standard deviation, median, range). The proportion of patients who achieve an undetectable PSA (≤ 0.2 ng/ml) after initiation of ipilimumab therapy will be provided with the exact 95% confidence interval. The Kaplan-Meier method will be used to estimate time to PSA progression, time to disease progression by any measure and time to death from any cause. In evaluation of time to PSA progression and time to disease progression by any measure will be censored for:

- 1) lost to follow-up at the date of last contact
- 2) use of additional cancer therapies that would interfere with ascertainment of the endpoint of interest
- death from a causes other than prostate cancer or treatment of prostate cancer.

Evaluation of time to death will be censored for lost to follow-up at last contact.

The effects of IRAEs and other immune parameters (e.g., a ratio of T regulatory cells to T effector cells) on clinical outcomes will be evaluated using logistic regression for binary endpoints (e.g., achievement of undetectable PSA) and Cox regression for the time to event outcomes (e.g., time to PSA progression).

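### Section 8.4 restricts the ITT analysis to patients whose endpoint was measured, so the reported primary proportion and CI are complete-case, while the go/no-go count stays on 30

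*Combined protocol and SAP*

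**What the plan says.** Section 8.4 defines the ITT population as "all patients who sign the consent and are assigned to a treatment regardless of the actual drug dose the patients receive". It then states when that population is used: "Whenever possible, we will use the ITT population to analyze the primary and secondary endpoints provided that their primary and secondary endpoints are measured". The per-protocol population, named as a secondary analysis, also removes patients who leave early. Neither planned analysis is therefore certain to keep every patient.

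Section 8.2 sets the endpoint: "The primary endpoint is the achievement of an undetectable PSA defined as" a value at or below 0.2 once ipilimumab has begun. Section 8.5 reports the proportion reaching that level "after initiation of ipilimumab therapy will be provided with the exact 95% confidence interval". It names no denominator and does not say how to classify a patient who has no such PSA. The synopsis repeats the Section 8.5 text. No section gives an imputation, replacement or non-responder rule.

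The decision rule in Section 8.3 is worded separately. Stage 2 needs at least two responders among the first 10, and for the final decision: "If 6 or more of 30 patients have achieved an undetectable PSA at 6 months, the study will be considered successful". The target rate there is "30% among patients treated with ipilimumab", which describes treated rather than assigned patients.

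**The concern.** In a single-arm trial the response rate and its interval are the main efficacy result. A patient who was registered but never dosed, or who left before any on-treatment PSA, has not been shown to respond. Under the proviso he leaves the denominator instead of counting as a failure, yet the result still carries the ITT label. For a fixed number of responders, a smaller denominator can only raise the reported rate.

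The success rule, in contrast, is a count out of 30. The published rate and the published decision could therefore describe different sets of patients. The plan also does not define what counts as measured, so that choice could be made after open-label PSA results are known.

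**Working it through.** **1. The plan's own design figures.** Inputs from Section 8.3: stage 1 of 10 with at least 2 responders to continue; total 30 with at least 6 for success; rates 10% and 30%.

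P(success) = sum over x = 2 to 10 of b(x; 10, p) × P(X2 ≥ 6 − x), with X2 ~ Bin(20, p).

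- p = 0.10: 0.0525 (stated type I error 0.05)
- p = 0.30: 0.8146 (stated power 0.80)

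The power is reproduced, and the type I error is slightly above its stated value. These figures use denominators of 10 and 30 throughout. An unmeasured patient adds nothing to either count, so the rule already treats him as a non-success.

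**2. Who is lost under the Section 8.5 window.** The Section 6.1 schedule has PSA at weeks 4, 7, 10, 12, 18 and 23/24. Early loss through progression is limited: "Progression will not be assessed until completion of the initial 4 cycles of treatment" (Section 3.5), and "all radiographic progression must be confirmed by a repeat scan done at least 4 weeks after the suspicious scan" (Section 5.1.4). Section 5.1.4 also withdraws patients for adverse events or withdrawn consent. Even so, a patient who has attended week 4 should already have one on-treatment PSA. If any PSA after the first dose suffices, those lost are mainly patients with none.

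**3. Effect on the estimate.** The documents give no missing rate, so 0 to 2 of 30 unmeasured (at most 2/30 = 6.7%) is an assumption. The unmeasured are taken to be non-responders. Exact 95% limits for x of n are the 0.025 quantile of Beta(x, n − x + 1) and the 0.975 quantile of Beta(x + 1, n − x).

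| Unmeasured (assumed) | 6 responders | 5 responders |
|---|---|---|
| 0 | 6/30 = 20.0% (7.7 to 38.6) | 5/30 = 16.7% (5.6 to 34.7) |
| 1 | 6/29 = 20.7% (8.0 to 39.7) | 5/29 = 17.2% (5.9 to 35.8) |
| 2 | 6/28 = 21.4% (8.3 to 41.0) | 5/28 = 17.9% (6.1 to 36.9) |

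The largest shift with 6 responders is 21.4 − 20.0 = 1.4 percentage points. The full-denominator interval is 38.6 − 7.7 = 30.9 points wide.

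**4. Estimate against decision.** With 5 responders the count rule fails. Within the assumed range the reported rate stays below 20.0%. It reaches 20.0% only with 5 unmeasured: 5/25 = 20.0% (6.8 to 40.7), the same rate as a passing 6/30. That lies outside the assumed range, but it shows how the two could disagree.

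**The case against.** The strongest reply is that this is a wording matter. The decision rule has fixed denominators, Section 8.5 does not test the interval against 10%, and the shift of at most 1.4 points is small beside an interval about 31 points wide. Measured is undefined, and if any on-treatment PSA qualifies, the analysis is close to full ITT. The phrase about treated patients in Section 8.3 describes the alternative hypothesis rather than an analysis set, and differs from ITT only for a registered patient who is never dosed. All of this stands as to size. It does not remove the defect: Section 8.4 states an exclusion, and nothing elsewhere overrides it for the estimate.

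A reader might infer three stronger points that the documents do not support.

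- **That the go/no-go decision is inflated.** It is not. An unmeasured patient cannot supply one of the 2 or the 6 responders.
- **That patients withdrawn before week 24 drop out of the estimate.** Six such losses would give 6/24 = 25.0% (9.8 to 46.7). But the 6-month wording belongs to the success count, whereas Section 8.5 defines the reported proportion from the start of ipilimumab. The 6-month wording can also be read as cumulative. Under a landmark reading even the direction would be uncertain, since an early responder who was withdrawn could be lost too.
- **That counting unmeasured patients as failures costs power.** If the 30% rate held only among measured patients and 5% were unmeasured independently of response, the effective rate would be 0.30 × 0.95 = 0.285 and power 0.777. That is already so under the rule as written, and editing Section 8.4 does not change it.

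**Conclusion.** The point holds for the reported proportion and its exact CI only. As written they are complete-case under an ITT label, and they can rest on a different denominator from the decision. On the Section 8.5 window, the rate at the success boundary is overstated by at most 1.4 points compared with counting every patient. This assumes that 0 to 2 of 30 are unmeasured, that all are non-responders, and that any on-treatment PSA counts as measured. The effect would be larger only if measured were taken to require a PSA at a 6-month landmark. Confidence is high that the rule is as described. The size cannot be fixed from the documents, because no missing rate is given. Severity is minor to moderate.

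**What to change.** In Section 8.4, delete the measured-endpoint proviso for the primary endpoint. Name one fixed denominator: all ITT patients as defined there, or all treated patients to match Section 8.3. Then add text such as:

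> Any patient in this denominator with no PSA ≤ 0.2 ng/mL in the endpoint window, for any reason including no PSA drawn, is a non-responder in the reported proportion and its exact 95% CI. An analysis of measured patients only is a sensitivity analysis.

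State one endpoint window and use it both for the estimate (Sections 8.2 and 8.5) and for the count rule (Section 8.3). Carry the same text into the synopsis.

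The cost is a few sentences, with no extra visits, PSA draws or patients. The reported rate may be slightly less favourable. Counting unmeasured patients as non-responders in the estimate does not change the operating characteristics of the count rule.

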8.5 Statistical Analysis Plan

Demographic and clinical characteristics will be summarized using descriptive statistics (e.g. proportions, mean, standard deviation, median, range). The proportion of patients who achieve an undetectable PSA (≤ 0.2 ng/ml) after initiation of ipilimumab therapy will be provided with the exact 95% confidence interval. The Kaplan-Meier method will be used to estimate time to PSA progression, time to disease progression by any measure and time to death from any cause. In evaluation of time to PSA progression and time to disease progression by any measure will be censored for:

- 1) lost to follow-up at the date of last contact
- 2) use of additional cancer therapies that would interfere with ascertainment of the endpoint of interest
- death from a causes other than prostate cancer or treatment of prostate cancer.

Evaluation of time to death will be censored for lost to follow-up at last contact.

The effects of IRAEs and other immune parameters (e.g., a ratio of T regulatory cells to T effector cells) on clinical outcomes will be evaluated using logistic regression for binary endpoints (e.g., achievement of undetectable PSA) and Cox regression for the time to event outcomes (e.g., time to PSA progression).

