Patients with a life expectancy less than 6 months, treatment with any investigational agent in the last 28 days, more than 18 months since initiation of AST, or a concurrent active malignancy diagnosed within the last 5 years (other than non-melanoma skin cancer, or other readily treatable tumors with expected cure) will not be eligible for this study. Patients must not have a known autoimmune disease, use prednisone > 10 mg daily (or its equivalent) orally for any indication, or have chronic infections (including hepatitis B or C or HIV).

Criteria for Evaluation: (Efficacy, safety, stopping rules, etc.)

Patients will receive a history and physical exam and multiple laboratory tests (PSA, complete chemistry panel and blood counts, as well as tests for endocrinopathies) at baseline and every 3 weeks during the first 4 doses of therapy. Available labs (i.e. the chemistry panel and blood counts) will be reviewed prior to administration of ipilimumab. Imaging studies will be done at baseline, 12 weeks, 24 weeks and then every six months, or sooner if concerning symptoms arise. If there is no evidence of radiographic progression on the 24-week scan, patients will go on to receive four doses of maintenance ipilimumab therapy (weeks 24, 36, 48, 60). They will have a history and physical exam at least every three months. Their survival status will be assessed by phone survey every 6 months for up to five years after the last study visit.

Efficacy will be based on the results of the PSA and imaging studies (using PCWG2 and modified RECIST criteria). Safety will be monitored using the regular physician examinations and laboratory assessments.

Statistics:

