N=30 (for the final analysis, 10 for the intial analysis). Using the Simon two-stage design for Phase II trials, the initial accrual will be 10 patients. Assuming that 10% of patients receiving usual care will achieve an undetectable PSA without additional intervention, the trial has a 80% power to detect a rate of achieving an undetectable PSA of \geq 30% among patients treated with ipilimumab. At least two patients with an undetectable PSA will be required in the first 10 patients to continue to stage 2. As soon as two patients achieve an undectable PSA, stage 2 for of the study will begin. If 6 or more of 30 patients have achieved an undetectable PSA at 6 months, the study will be considered successful and the regimen worthy of further investigation. This design has a type I error rate of 0.05 and a type II error rate of 0.20.

Demographic and clinical characteristics will be summarized using descriptive statistics (e.g. proportions, mean, standard deviation, median, range). The proportion of patients who achieve an undetectable PSA (≤0.2 ng/ml) after initiation of ipilimumab therapy will be provided with the exact 95% confidence interval. The Kaplan-Meier method will be used to estimate time to PSA progression, time to disease progression by any measure and time to death from any cause. In evaluation of time to PSA progression and time to disease progression by any measure will be censored for: (1) lost to follow-up at the date of last contact, (2) use of additional cancer therapies that would interfere with ascertainment of the endpoint of interest (3) death from causes other than prostate cancer or treatment of prostate cancer. Evaluation of time to death will be censored for lost to follow-up at last contact.

The effects of IRAEs and other immune parameters (e.g., a ratio of T regulatory cells to T effector cells) on clinical outcomes will be evaluated using logistic regression for binary endpoints (e.g., achievement of undetectable PSA) and Cox regression for the time to event outcomes (e.g., time to PSA progression).

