1.4 Overall Risk/Benefit Assessment melanoma and prostate cancer

Results from the 3 primary efficacy studies of ipilimumab suggest that the 10 mg/kg dose is active and offers the best benefit to risk ratio based on a 27.1% to 35.1% rate of disease control and a favorable 1-year survival rate of 48.6% to 59.1% compared with that reported in the literature (25.5% to 35%). ^{24,25,26,27} Substantial reductions in total tumor burden, including widely disseminated disease in the skin, lung, and/or other visceral

disease sites, were reported. More than half the responses were reported in subjects staged with M1b or M1c advanced melanoma disease, which is most resistant to approved therapies. The kinetics of ipilimumab resulted in known patterns of clinical activity (CR, PR and SD) as well as novel patterns, characterized by reductions in total tumor burden, including existing and new lesions, after initial tumor volume increase and/or after appearance of new lesions. In the pretreated population at 10 mg/kg in 2 of the 3 studies, disease control after initial tumor volume increase and/or new lesions was reported for 9.7% of subjects. Across all 3 studies, stable disease was often accompanied by clinically relevant reductions in tumor burden compared to baseline. All patterns of response, including SD, appeared to result in favorable survival, based on 1-year survival rates.

Characteristic organ-specific inflammatory IRAEs were reported with ipilimumab therapy, typically during induction therapy. IRAEs were mostly reversible within days to weeks following cessation of therapy or treatment with symptomatic therapy, corticosteroids or other anti-inflammatory agents, depending upon severity. Accumulated clinical experience resulted in detailed toxicity management guidelines (also termed algorithms), by use of which IRAEs can be effectively managed, especially when IRAEs are recognized early and subjects are treated in a timely fashion. This can minimize the occurrence of IRAE complications, such as GI perforation/colectomy or hepatic failure.

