2.2 Secondary Objectives

- Time to PSA progression
- Time to progression by any measure
- Maximum percentage of PSA reduction in each patient
- Number of patients with IRAEs and correlation of these with complete PSA response, time to progression, and T cell measurements
- Measures of T cell response to therapy with flow cytometry
- Response in Measurable disease by modified RECIST criteria
- Time to death from any cause.
- To examine correlative biomarkers and their relationship to clinical outcomes. Potential biomarkers include, but are not limited to CRP, IGF-1 and -2, or FSH.
- Bank samples for future molecular correlative studies, biomarker, or other studies.

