5 STUDY THERAPY

All patients will receive ipilimumab 10 mg/kg IV over 90 minutes on day 1 of each 21-day cycle for four cycles. Those patients who have not progressed (radiographically) will also receive the same dose of ipilimumab once every three months for an additional four doses. Each patient's available lab results (i.e. chemistries and blood counts) will be reviewed prior to each ipilimumab infusion.

5.1 **Ipilimumab**

Each patient will receive ipilimumab 10 mg/kg IV over 90 minutes (not bolus or IV push).

Ipilimumab (BMS-734016) is a human immunoglobulin G (IgG1) κ anti-CTLA-4 monoclonal antibody (mAb). In vitro studies were performed with ipilimumab to demonstrate that it is specific for CTLA-4, actively inhibits CTLA-4 interactions with B7.1 and B7.2, does not show any cross-reactivity with human B7.1, B7.2 negative cell lines, and stains the appropriate cells without nonspecific cross-reactivity in normal human tissues, as demonstrated by immunohistochemistry. Ipilimumab does cross-react with CTLA-4 in non-human primates, including cynomolgus monkeys.

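### Section 8.5 does not tie IRAE status to its onset in the Cox models; a fixed ever-IRAE term would lean towards later progression if some first IRAEs arise in maintenance (cheap improvement, low stakes)

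*Combined protocol and SAP*

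**What the plan says.** Section 8.5 plans to relate "The effects of IRAEs and other immune parameters" to clinical outcomes by logistic regression for binary endpoints and "Cox regression for the time to event outcomes (e.g., time to PSA progression"). The synopsis repeats this: "using logistic regression for binary endpoints (e.g., achievement of undetectable PSA) and Cox regression for the time to event outcomes". Neither place, nor any other section, gives a time-dependent covariate, a landmark or a cut-off for counting IRAEs.

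The analysis serves a listed objective in section 2.2: "Number of patients with IRAEs and correlation of these with complete PSA response, time to progression, and T cell measurements".

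Maintenance dosing depends on the outcome. Section 5: "Those patients who have not progressed (radiographically) will also receive the same dose of ipilimumab once every three months for an additional four doses". The synopsis agrees: "If there is no evidence of radiographic progression on the 24-week scan, patients will go on to receive four doses of maintenance ipilimumab therapy". So does section 3.5: "Patients who progress radiographically on ipilimumab after completion of the initial four doses will not receive more immunotherapy once progression has been documented". By contrast, section 3.5 defers progression assessment until the four induction cycles are complete.

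On timing, section 1.4 reports: "Characteristic organ-specific inflammatory IRAEs were reported with ipilimumab therapy, typically during induction therapy". Section 7.3 requires the onset of every adverse event to be captured.

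**The concern.** An IRAE happens after baseline, so a Cox model containing it is incomplete until the plan says from when a patient counts as exposed. The simplest coding is one yes/no value per patient for the whole follow-up. Under this dosing rule, a man who progresses at the Week 12 or Week 24 scan receives no maintenance, while one who stays free of progression can receive four more doses and may have his first IRAE then. A fixed term credits that IRAE with the progression-free months that came before it. This is immortal-time bias, and its direction is known: IRAE patients appear to progress later.

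What is at stake is one secondary objective. Section 1.3.6.1 describes the earlier evidence on IRAEs and response as inconclusive, so an analysis that can create the association by itself would not help to settle it.

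**Working it through.** The documents give no power, precision or expected effect for this analysis, so there is no stated figure to reproduce.

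**Inputs from the documents.** N=30 (8.3). Maintenance at weeks 24, 36, 48 and 60 (synopsis). Scans at weeks 12 and 24, then three-monthly (3.3; the synopsis evaluation paragraph and 6.4.2 say six-monthly). Any-grade IRAE rate 54.0% (1.3.6.1), about 60% (1.3.5), 70.4% at 10 mg/kg (Table 1) and 74% (5.1.7.1).

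**Assumptions not in the documents.** Median time to radiographic progression 26 to 52 weeks, and the rate of first IRAEs in maintenance.

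**Step 1: the mechanism.** Suppose 60% have an IRAE in induction and each maintenance dose carries first-IRAE risk q. The chance of being ever-IRAE after k maintenance doses is 1 − 0.40 × (1 − q)^k.
- k = 0: 60% for any q.
- k = 4, q = 5%: 1 − 0.40 × 0.8145 = 67.4%.
- k = 4, q = 10%: 1 − 0.40 × 0.6561 = 73.8%.
- k = 4, q = 20%: 1 − 0.40 × 0.4096 = 83.6%.

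The label therefore depends on how long the patient stayed progression-free, although IRAEs do nothing to progression here.

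**Step 2: size for radiographic progression, true HR = 1.** Two simulations with different structures were run.

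*Simulation A.* IRAE hazard in maintenance is a ratio r of the induction hazard; 54 to 74% ever have an IRAE.

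| r | First IRAEs after Week 12 | HR, fixed term | False positives, N=30 (nominal 5%) |
|---|---|---|---|
| 0 | not applicable | 0.99–1.00 | 5–8% |
| 0.05 | 4–7% | 0.90–0.95 | 6–8% |
| 0.10 | 7–14% | 0.83–0.91 | 7–10% |
| 0.25 | 16–29% | 0.69–0.83 | 11–21% |

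*Simulation B.* Risk q per maintenance dose; 60% induction IRAE rate.

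| q | First IRAEs in maintenance | HR, fixed term | False positives, N=30 |
|---|---|---|---|
| 0 | 0% | 1.00–1.01 | 5–7% |
| 5% | 4–7% | 0.89–0.90 | about 7% |
| 10% | 8–12% | 0.80–0.81 | 10–12% |
| 20% | 13–19% | 0.63–0.65 | about 24% |

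The low and middle rows of both give about 0.8 to 0.95. The share of late first IRAEs does not fix the size by itself. In B a 13% share gave 0.65 at q = 20%; with a 30% induction rate a 14% share gave 0.82. The bottom rows are upper cases, given what section 1.4 says about timing.

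**Step 3: other endpoints, fixed term.**
- Progression by any measure (B; q = 5, 10, 20%): HR 0.91–0.92, 0.83, 0.69–0.71.
- PSA progression (A; r = 0.05, 0.10, 0.25): 0.98–1.02 throughout if independent of radiographic progression; 0.95–0.99, 0.91–0.94, 0.87–0.92 at correlation 0.5.
- PSA response (A): spurious odds ratio 1.05–1.10, 1.09–1.18, 1.16–1.43, and only if responders' median time to progression is two to three times longer.

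**Step 4: against sampling error.** With 30 events and a 60/40 split, SE(log HR) = 1/√(30 × 0.6 × 0.4) = 0.373. The null 95% interval is exp(±1.96 × 0.373) = 0.48 to 2.08. Biased HRs of 0.95, 0.90 and 0.83 lie 0.14, 0.28 and 0.50 standard errors from 1. For PSA response with 6 responders, 24 non-responders and 60% IRAE in each, SE = √(1/3.6 + 1/2.4 + 1/14.4 + 1/9.6) = 0.93, an interval of about 0.16 to 6.2.

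**Step 5: alternatives.** For radiographic progression, a time-dependent term gave HR 0.99–1.02 and the Week 12 landmark 0.99–1.02. For PSA progression correlated with radiographic progression and followed past it, the time-dependent term stayed slightly low (0.89–0.99), because the dosing gate is itself prognostic; the landmark gave 0.98–1.02. Week 12 status in all patients also gave 0.98–1.02. Time to death was not simulated.

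**The case against.** The strongest reply is that this is an omission, not an error. Cox regression accommodates a time-dependent covariate as readily as a fixed one. A reader might infer that the plan commits to an ever/never term; it does not, and every biased figure above is conditional on that coding. This stands.

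The key input is also missing. The documents do not give the share of first IRAEs arising in maintenance, and section 1.4 points to a low one. The simulations leave out dose skipping and discontinuation for adverse events (5.1.3 to 5.1.5) and censoring at additional cancer therapy (8.5). At the more plausible low rates the bias is a fraction of a standard error. The plan's named example, time to PSA progression, does not gate dosing. All of this stands and keeps the stakes low. It does not supply the missing rule.

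A reader might also infer that the bias would come from the extra dosing alone, because adverse events are recorded as they occur. That instruction sits in section 3.3.1 and covers only the first four doses. As extracted, the section 6.1 schedule has no adverse-event entry at weeks 12, 18 or 23/24 and resumes at the Week 24 dosing visit. Sections 6.2.1 and 7.3.3 give some cover, and table extraction may be imperfect, but uneven recording after induction cannot be ruled out as a further contributor.

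**Conclusion.** The concern holds as a cheap, low-stakes improvement. Section 8.5 leaves IRAE timing open in a design where later exposure depends on being free of radiographic progression. If a fixed ever-IRAE term is used and some first IRAEs arise in maintenance, the HR for radiographic or any-measure progression is biased below 1: about 0.8 to 0.95 in the low-to-middle scenarios, and about 1.0 if all first IRAEs fall in induction. The direction follows from the dosing rule; the size rests on assumed progression times and maintenance IRAE rates.

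The documents do not support a stronger reading, namely that the analysis is certain to mislead or that the bias would dominate the result at N=30. For PSA progression the bias needs correlation with radiographic progression; for PSA response it is negligible beside sampling error. The 6-of-30 success rule and patient safety are not touched.

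**What to change.** Add to section 8.5 and the matching synopsis text:

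*In Cox models IRAE status is fixed at Week 12 (onset by Week 12) and analysed as a Week 12 landmark in patients event-free at Week 12. For time to radiographic or any-measure progression, IRAE is also entered as a time-dependent covariate from its onset date. For PSA response, the planned logistic regression uses IRAE onset by Week 12.*

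The landmark leads because it stayed unbiased for PSA progression, where the time-dependent term did not fully do so.

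The cost is a few sentences and a few lines of code, with no new data, since onset is already captured. The landmark ignores later IRAEs and drops patients with events by Week 12. For radiographic progression that is 30 × (1 − 2^(−12/52)) = 4.4 to 30 × (1 − 2^(−12/26)) = 8.2 patients, or about 4 to 8 of 30. For PSA progression it was 6 to 14 of 30 in simulation. A sensitivity analysis using Week 12 IRAE status in all patients can be shown alongside. It is reasonable because induction generally continues despite early radiographic progression (3.5, 6.4.4), although section 6.4.4 excepts rapid clinical deterioration.
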